3.3 Dose Limiting Toxicity Definitions

The DLT evaluable population is defined as those subjects in Part 1 fulfilling the 'All Subjects' population criteria and having received an adequate treatment in the first 28 days to enable an appropriate evaluation of study drug related DLTs. Adequate exposure during the first 28 days

will be defined as having received >75% of planned study drug doses, exclusive of missed doses due to treatment-related toxicity. For those subjects who are either withdrawn or dose reduced due to toxicity during the first 28 days will be included in the DLT evaluable population.

An AE will be considered a DLT if it occurs within the **first 28 days of treatment** with dabrafenib, and if it is considered by the investigator to be related to treatment with dabrafenib, and if meets at least one of the following additional criteria:

- Grade 4 hematologic AE (specifically neutropenia, anemia, thrombocytopenia and lymphopenia);
- Grade 3 or 4 non-hematologic AE. Grade 3 nausea, vomiting, and diarrhea will only be considered dose limiting if uncontrolled with standard supportive measures. Cutaneous SCC is not considered a DLT;
- Treatment delay of greater than 7 consecutive days due to unresolved AE
- Ejection fraction less than the lower limit of normal (LLN) with an absolute decrease of >10% from baseline with confirming assessment within 7 days;
- A Grade 2 or greater non-hematological AE that in the judgment of the investigator and Novartis Medical Lead is dose limiting;
- AEs requiring a dose reduction.

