3.7.4 Dose Modification Guidelines - Adverse Events of Special Interest

3.7.4.1 Pyrexia

Pyrexia has been observed in adult subjects receiving dabrafenib. In a minority of cases pyrexia was accompanied by symptoms such as severe chills/rigors, dehydration, and hypotension, which in some cases can lead to acute renal insufficiency. Serious non-infectious febrile events have been observed and typically occurred within the first month of therapy.

Subjects should be instructed on the importance of immediately reporting febrile episodes. Therapy with dabrafenib should be interrupted if the patient's temperature is $\geq 38.5^{\circ}\text{C}$ or 101.3° Fahrenheit. In the event of a fever, the subject should be instructed to take anti-pyretics (e.g. ibuprofen or acetaminophen/paracetamol as appropriate to control fever). The use of oral corticosteroids should be considered in those instances in which anti-pyretics are insufficient. In subjects experiencing pyrexia associated with rigors, severe chills, dehydration or hypotension, serum creatinine and other evidence of renal function (e.g. creatinine clearance, BUN) should be monitored carefully during and following severe events of pyrexia. Pyrexia accompanied by hypotension, dehydration requiring intravenous fluids, renal insufficiency and/or severe (\geq Grade 3) rigors/chills in the absence of an obvious infectious cause should be reported as a SAE.

Guidelines regarding management and dose reduction for pyrexia considered to be related to dabrafenib are provided in [Table 3-4](#).

Table 3-4 Mandatory Dose Modification and Recommended Clinical Management for Pyrexia

Occurrence ^{a,b}	Recommended adverse event management guidelines	Mandatory dose modification requirements
Any	
 ● Clinical evaluation for infection and hypersensitivity^c ● Laboratory (local lab) work-up^c ● Hydration as required^d 	
1st Event ^b :	
 ● Administer anti-pyretic treatment as clinically indicated and initiate prophylactic treatment if associated with rigors, renal failure, dehydration, or hypotension^e 	
 ● Interrupt dabrafenib ● Once pyrexia resolves to baseline, restart dabrafenib at the same dose level ● If fever was associated with dehydration, hypotension, or renal insufficiency, reduce dabrafenib to the next lower dose level. ^g

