2nd Event ^e	
 ● Same as for 1st event, and ● Within 3 days of onset of pyrexia 
 ● Optimize anti-pyretic therapy ● Consider oral corticosteroids for at least 5 days or as clinically indicated^f 	
 ● Same as 1st event.
Subsequent Events:	
 ● Within 3 days of onset of pyrexia 
 ● Optimize oral corticosteroid dose as clinically indicated for recalcitrant pyrexia^f ● If corticosteroids have been tapered and pyrexia recurs, restart steroids 	
 ● Interrupt dabrafenib ● Once pyrexia resolves to baseline, restart dabrafenib reduced by one dose level^g

- ^a. Pyrexia is defined as a body temperature equal to or above 38.5°C Celsius or 101.3°F Fahrenheit.
- ^b. For subjects experiencing pyrexia complicated by rigors, severe chills, etc., a clinical evaluation and laboratory work-up is mandatory for each event; anti-pyretic treatment should be started immediately at the first occurrence and prophylactic anti-pyretic treatment is recommended.
- ^c. Thorough clinical examination for signs and symptoms of infection or hypersensitivity is required; laboratory work up should include full blood count, electrolytes, creatinine, BUN, CRP, and liver function tests.
- ^d. Oral hydration should be encouraged in subjects without evidence of dehydration. Intravenous hydration is recommended in subjects experiencing pyrexia complicated by dehydration/hypotension.
- ^e. Anti-pyretic treatment may include acetaminophen (paracetamol), ibuprofen, or suitable anti-pyretic medication according to institutional standards. Prophylactic anti-pyretic treatment may be discontinued after three days in the absence of pyrexia
- ^f. In subjects experiencing pyrexia complicated by rigors, severe chills, etc., which cannot be controlled with anti-pyretic medication, oral corticosteroids should be started at the 2nd event and doses should be gradually increased for subsequent events.
- ^g. Dabrafenib should be reduced by one dose level after 3 episodes of pyrexia complicated by rigors, severe chills etc., which cannot be managed by best supportive care, including increasing doses of oral steroids. Re-escalation of dabrafenib is allowed if no episode of pyrexia is observed in the 4 weeks subsequent to dose reduction

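### Footnote g of the pyrexia table (Table 3-4) gives a different dose-reduction trigger from the mandatory cells it is attached to, most clearly for third and later events

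*Protocol*

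**What the plan says.** Table 3-4 (Protocol Section 3.7.4.1) separates recommended management from mandatory dose modification. The mandatory column reads as follows.

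- First event: "Once pyrexia resolves to baseline, restart dabrafenib at the same dose level". There is one exception, which carries marker g: "If fever was associated with dehydration, hypotension, or renal insufficiency, reduce dabrafenib to the next lower dose level".
- Second event: "Same as 1st event".
- Subsequent events, again with marker g: "Once pyrexia resolves to baseline, restart dabrafenib reduced by one dose level". No complication is required.

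Footnote g reads: "Dabrafenib should be reduced by one dose level after 3 episodes of pyrexia complicated by rigors", and the list continues with severe chills and an open-ended *etc.* It adds that these are episodes which best supportive care, including rising oral steroid doses, has not controlled. Its second sentence allows re-escalation after 4 weeks without fever.

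Section 3.3 lists "AEs requiring a dose reduction" among the DLT criteria. It applies to events within the first 28 days that the investigator considers related to dabrafenib, and the DLT evaluable population is confined to Part 1. Section 5.3.3.1 still plans a DLT summary. SAP Section 2.4 summarizes dose reductions, dose intensity and relative dose intensity.

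**The concern.** A footnote attached to a mandatory instruction should explain or limit it. Here it differs from its cells in three respects: how many episodes are needed, which complications count, and whether supportive care must first have failed. Two teams could therefore treat the same fever differently, and both could cite the same table.

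Pyrexia is common: Section 1.3 gives 27% in the adult safety population. Three things depend on the reading:

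- dose reductions in subjects still on treatment;
- the dose-reduction and relative dose intensity tables in the final report;
- because a required dose reduction is itself a DLT criterion, which Part 1 fevers in the first 28 days count as DLTs. The denominator can move too, since SAP Section 2.2.3 places subjects whose dose was reduced for toxicity in that window in the DLT evaluable population.

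**Working it through.** The plan states no figure on this point, so the check is mainly a comparison of the table with its footnote. All events are taken to be related to dabrafenib, as Section 3.7.4.1 requires for the table to apply.

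| Event | Mandatory cell | Footnote g | Result |
|---|---|---|---|
| 1st or 2nd, uncomplicated | same dose | trigger not met | agree |
| 1st or 2nd, rigors or severe chills only | same dose | count of 3 not reached | agree |
| 1st or 2nd, with dehydration, hypotension or renal insufficiency | reduce | not met if g limits the cell; silent if g only adds to it | depends on reading |
| 3rd or later, uncomplicated | reduce | trigger not met | differ |
| 3rd or later, complicated but controlled by supportive care | reduce | trigger not met | differ |
| 3rd or later, three complicated episodes, not controlled | reduce | reduce | agree |

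**Third and later events.** The disagreement does not depend on how the open-ended complication list is read. Nor does it help to treat g as an extra trigger. A third complicated episode is at least the third event, and the cell already requires a reduction there. So the first sentence of g either limits the cell, and the two disagree, or it adds nothing.

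**First and second events.** The cell names dehydration, hypotension and renal insufficiency. Footnote g names rigors and severe chills and ends in *etc.* The text supports either view. The opening of Section 3.7.4.1 groups chills or rigors with dehydration and hypotension as symptoms accompanying fever, and footnote d also calls dehydration and hypotension complications. Yet the first-event management cell lists rigors with the others, while the dose cell beside it leaves rigors out.

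**Subjects still exposed to the rule.** The Amendment 11 rationale gives 85 treated and 52 completed or discontinued at 17-Jul-2020: 85 − 52 = 33. The Amendment 10 rationale gives the same 52 for February 2019, so 33 is best read as an upper figure.

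**Part 1 DLT classification.** Part 1 enrolled 27 subjects. Let c be the share with a related event in the first 28 days whose DLT status turns on the reading. The documents give no value for c, so a range is assumed. The expected number is 27 × c, and the probability of at least one is 1 − (1 − c)^27.

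| Assumed c | Expected in 27 | P(at least one) |
|---|---|---|
| 2% | 0.54 | 0.42 |
| 5% | 1.35 | 0.75 |
| 10% | 2.70 | 0.94 |
| 20% | 5.40 | 0.998 |

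If c is taken as the rate of all such fevers, these are upper bounds. Some would be DLTs anyway under Section 3.3, for example as Grade 3 or 4 non-hematologic events or delays of more than 7 days.

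**The case against.** A reader might infer a flat contradiction at the first complicated fever, with one episode required by the cell and three by the footnote. The documents do not go that far. Footnote g says when the dose should be reduced; it does not say that earlier reduction is excluded. Its named complications differ from those in the cell, and for a first event with rigors alone the two agree. Its re-escalation sentence applies to any reduction and could explain why the marker sits on both cells. These points stand, and they make the first- and second-event issue an ambiguity.

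A reader might also infer that dose escalation is at risk. Under Appendix 1, with six subjects enrolled and no data pending, one DLT means escalate and two mean de-escalate. That example needs another DLT already in the cohort, and a related event that is not a DLT on any other criterion. Part 1 is closed, no MTD was established, and the recommended doses were set on exposure (Amendment 10 and 11 rationales). No escalation decision can now change, and nothing shows that dose selection was wrong.

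Three further points reduce the size:

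- Section 3.7 has the sponsor's Medical Lead make all dose adjustments with the investigator, which limits divergence between sites. Section 3.7.3.1 also refers to further guidance in the Study Procedures Manual, which is not available here.
- Table 3-5 separately governs creatinine rises of 50% or more, so some renal cases do not turn on footnote g.
- The 27% covers all adult pyrexia. Section 1.3 describes 94% of events (55% + 39%) as Grade 1 or 2, and Section 3.7.4.1 calls complicated cases a minority.

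None of these removes the mismatch for third and later events.

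**Conclusion.** The point holds as an internal inconsistency in a mandatory table. It is clear for events after the second and ambiguous for the first two. It bears on dosing for at most about 33 subjects at the July 2020 count, on the dose-reduction and relative dose intensity summaries, and on the descriptive DLT summary for 27 Part 1 subjects.

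The number of Part 1 classifications affected cannot be found from the documents. The range of about 0.5 to 5.4 rests wholly on the assumed 2% to 20%. The DLT consequence is limited to related events in the first 28 days of Part 1 that meet no other DLT criterion. The conclusion requires no view on which trigger is clinically right.

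**What to change.** Reconcile the Table 3-4 cells with footnote g so that one consistent reduction trigger remains for each row. The text should settle:

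- whether footnote g limits the cells or adds to them;
- whether its complication list includes dehydration, hypotension and renal insufficiency;
- whether failure of supportive care is a condition;
- whether the re-escalation sentence applies to every reduction. If it does, it could stand as a separate note.

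The clinical choice belongs to the sponsor and investigators. Any matching guidance in the Study Procedures Manual should be brought into line.

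In the SAP or study report, state which reading was used to classify Part 1 DLTs, and list the Part 1 subjects with a related pyrexia in the first 28 days whose DLT status depends on it.

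The cost is protocol wording, a sentence in the SAP or report, and a check of fever events and dose reductions already recorded for 27 subjects. No new data are needed.

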3.7.4.2 Renal insufficiency

Cases of renal insufficiency have occurred in adult subjects receiving dabrafenib. Prior to start of study treatment, concomitant medications must be reviewed for the potential risk of inducing nephrotoxicity and concomitant medications may be modified if clinically possible.

Guidelines regarding management and dose reduction for renal insufficiency considered to be related to study treatment by the investigator are provided in [Table 3-5](#).

Table 3-5 Mandatory Dose Modification and Required Clinical Management Guidelines for Renal function alterations

For subjects with creatinine rise \geq 50% from baseline :	Required adverse event management guidelines	Mandatory dose modification requirements
1 st occurrence	
 ● If subject has fever: treat pyrexia as per Table 5 (please note NSAIDs can induce renal insufficiency, especially in subjects with dehydration); consider IV hydration ● Pediatric nephrology consult is recommended ● Re-check within 24 hours ● If creatinine rise is < 25% from baseline: ● Monitor creatinine weekly for 4 weeks to ensure levels remain within 25% of baseline ● If creatinine rise is \geq 25% but < 50% from baseline: 
 ● Monitor creatinine at least twice weekly, can decrease frequency if creatinine rise < 25% from baseline ● Avoid nephrotoxic agents ● If creatinine rise is \geq 50% but < 100% from baseline: 
 ● Monitor creatinine at least twice weekly ● Avoid nephrotoxic agents 	
 ● If creatinine rise is < 25% from baseline: Continue dabrafenib at current dose ● If creatinine rise is \geq 25% but < 50% from baseline: 
 ● Continue dabrafenib at current dose ● If creatinine rise is \geq 50% but < 100% from baseline: 
 ● Interrupt dabrafenib ● May restart dabrafenib at reduced dose if creatinine rise returns to < 25% from baseline ● If creatinine rise is \geq 100% from baseline, permanently discontinue dabrafenib
2nd occurrence	
 ● See guidance for first occurrence 	
 ● Permanently discontinue dabrafenib

3.7.4.3 Dose Modifications and Management Guideline for New Malignancies

CuSCC

Cases of cuSCC (which include those classified as keratoacanthoma or mixed keratoacanthoma subtype) have been observed in subjects treated with dabrafenib. Approximately 70% of events occurred within the first 12 weeks of treatment with a median time to onset of 8 weeks. These should be surgically removed according to institutional practices. Dose modification or interruption of study treatment is not required for cuSCC or KA, however cuSCC should be reported as an SAE (refer to [Section 11.7](#)). [REDACTED]

Patients should be instructed to immediately inform their physician if new lesions develop. Skin examination should be performed prior to initiation of dabrafenib and during treatment with dabrafenib, every 2 months throughout therapy. Monitoring of the skin should continue every 2 to 3 months for 6 months following discontinuation of dabrafenib or until initiation of another

anti-neoplastic therapy. Monitoring of the skin can be performed by a qualified local physician (e.g. subject’s general practitioner) at the discretion of the investigator during non-clinic visits or visits where only dermatologic assessment is to be performed and subject has extensive travel requirement. If possible, the same local physician should perform each exam throughout the study to ensure consistency between evaluations.

New Primary Melanoma

New primary melanomas have been reported in patients treated with dabrafenib. These were identified primarily within the first 5 months of therapy and did not require treatment modification other than excision. Monitoring for skin lesions should occur as described for cuSCC.

Non-Cutaneous Malignancies

In vitro experiments have demonstrated paradoxical activation of MAP-kinase signalling in BRAF wild type cells with RAS mutations when exposed to BRAF inhibitors, which may lead to increased risk of non-cutaneous malignancies in patients treated with dabrafenib (Sievert, 2013). Cases of RAS-driven malignancies have been seen with BRAF inhibitors. Patients should be monitored as clinically appropriate.

Following discontinuation of dabrafenib, monitoring for non-cutaneous secondary/recurrent malignancies should continue for up to 6 months or until initiation of another anti-neoplastic therapy.

New non-cutaneous malignancies should be reported as a SAE.

Refer to [Appendix 6](#) for French country specific dermatological follow up.

3.7.4.4 Guidelines for prolonged QTc

Guidelines for dose modification and stopping criteria due to QTc-prolongation are provided in [Table 3-6](#).

Table 3-6 Withholding and Stopping Criteria for QTc-Prolongation

QTc Prolongation	Required adverse event management guidelines	Mandatory dose modification requirements
QTcB ≥501 msec	
 • Test serum potassium, calcium, phosphorus and magnesium. If abnormal, correct per routine clinical practice to within normal limits. • Review concomitant medication usage for agents that prolong QTc 	
 • Interrupt study treatment (dabrafenib) until QTcB prolongation resolves to grade 1 or baseline • If event resolves to grade 1 or baseline, restart study treatment at current dose level • If event does not resolve, permanently discontinue study treatment.

	
 Consider evaluation with cardiologist (recommended). 	
 If event recurs, permanently discontinue study treatments.

Abbreviations: ECG = electrocardiogram; msec = milliseconds; QTcB = QT duration corrected for heart rate by Bazett's formula.
 
a. Based on average QTc value of triplicate ECGs. For example, if an ECG demonstrates a prolonged QT interval, obtain two or more ECGs over a brief period, and then use the averaged QTc values of the three ECGs
		

3.7.5 Management Guidelines for Additional AEs

- Palmar Plantar Erythrodysesthesia (PPES)** – Measures for PPES should include:
 - Lifestyle modification: avoidance of hot water, traumatic activity, constrictive footwear, or excessive friction on the skin and the use of thick cotton socks and gloves, and shoes with padded insoles
 - Symptomatic treatments: apply moisturizing creams frequently, topical keratolytics (e.g. urea 20-40 % cream, salicylic acid 6%, tazarotene 0.1% cream, fluorouracil 5% cream), clobetasol propionate 0.05% ointment for erythematous areas, topical lidocaine 2%, and / or systemic pain medication such as nonsteroidal anti-inflammatory drugs, codeine, and pregabalin for pain.
 - Dose modification may also be required.
- Pancreatitis** – In the event of abdominal pain or suspected pancreatitis, amylase and lipase laboratory samples should be collected for confirmation of the diagnosis. Patients should be closely monitored when re-starting dabrafenib after an episode of pancreatitis
- Uveitis:** Treatment with dabrafenib has been associated with the development of uveitis, including iritis. Monitor patients for visual signs and symptoms (such as, change in vision, photophobia and eye pain) during therapy. Permanently discontinue dabrafenib for persistent \geq grade 2 uveitis (including iritis and iridocyclitis) of $>$ 6 week duration.
- Hyperglycemia:** Hyperglycemia requiring an increase in the dose of, or initiation of insulin or oral therapy can occur with dabrafenib. Monitor serum glucose levels as clinically appropriate during treatment with dabrafenib in subjects with pre-existing diabetes or hyperglycemia. Advise patients to report symptoms of severe hyperglycemia such as excessive thirst or any increase in the volume or frequency of urination.

3.7.6 Left Ventricular Ejection Fraction Stopping Criteria

ECHO must be performed at baseline and at follow-up visit(s) per the schedule in the Time and Events Table. Subjects who have an asymptomatic, absolute decrease of $>10\%$ in LVEF compared to baseline **and** the ejection fraction is below the institution's LLN should temporarily discontinue dabrafenib and have a repeat evaluation of LVEF within 1 week. ECHO should be repeated every 1-2 weeks for 4 weeks or until LVEF recovery to above institutional lower limit of normal and within 10% of baseline.

- If the LVEF recovers (defined as \geq LLN **and** absolute decrease $\leq 10\%$ compared to baseline) at any time during the next 4 weeks, **after consultation and approval of the Medical Lead**, the subject may be restarted on dabrafenib at a reduced dose(s). For such subjects, monitoring of LVEF will then be performed 2 and 4 weeks after rechallenge, and every 4 weeks thereafter for 12 weeks and then per protocol.

- If repeat LVEF does not recover within 4 weeks, then the subject should permanently discontinue dabrafenib. Ejection fraction should continue to be monitored every 4 weeks for 16 weeks or until resolution.

Subjects with a Grade 3 or 4 (symptomatic) left ventricular systolic dysfunction must discontinue dabrafenib. Ejection fraction should continue to be monitored every 4 weeks for 16 weeks or until resolution. If recovery occurs (LVEF to above institutional LLN and symptom resolution) within 4 weeks, the subject may restart dabrafenib at a reduced dose in consultation with the Medical Lead (if in the opinion of the investigator, the subject was receiving or likely to receive clinical benefit with continued treatment).

All events of LVEF meeting the stopping criteria should be reported as SAEs (refer to [Section 11.7](#)).

Copies of all ECHO(s) will be required for possible central review. Copies of all cardiology consultations performed on subjects who experience a >10% decrease in LVEF from baseline and whose cardiac ejection fraction is below the institution's LLN will also be required for possible central review. Details for central collection of ECHOs will be provided in the SPM.

